	1 Day 3-hours	Day 1 7-9 hours	Day 2 optional	1 Day 1-hour	Day 1 7-9 hours	Day 2 optional
Procedures	Screening	Baseline		Compliance (Outpatient)	Outcome	
Informed Consent	X					
History and Physical (MMSE Visit 1 only)	X				X	
Review Inclusion/Exclusion Criteria	X	X				
Symptoms Review Questionnaire	X	X			X	
PANAS, RAND SF-36		X		X	X	
Cognitive Testing		X			X	
MRI		X			X	
Accelerometers	X				X	
Vital Signs	X	X		X	X	
Anthropometric measurements	X	X		X	X	
Urine Drug Screen	X					
Urine Pregnancy test	X	X			X	
Fasting Blood Draw	X	X		X	X	
Mixed Meal Tolerance Test		X			X	
Lumbar Puncture		X			X	
Dispense Diet Shakes (5-2 CR Group)		X		X		
Dietary Counseling-ALL Groups		X		X		
Meals / Snacks		X		X	X	
Follow-up Phone Call or Email				Weeks 1, 3, 5, 7	Follow-up	
Payment	\$50.00	\$350.00		\$150.00*	\$500.00	

Table 2: Laboratory

	Visit 1	Visit 2		Visit 3, 4, 5	Visit 6	
		Week 0		Weeks 2, 4, 6	Week 8	
	1 Day 3-hours	Day 1 7-9 hours	Day 2 optional	1 Day 1-hour	Day 1 7-9 hours	Day 2 optional
Laboratory	Screening	Baseline within 4 weeks of Screening Visit		Compliance (Outpatient)	Outcome	
Clinical Labs: CBC with differential, CMP, HbA1c, Phosphate, Magnesium, TSH, Liver Panel, Lipid Panel, Uric Acid, PT/INR, PTT, insulin, HIV, HBV, HCV	X					
Research Lab: Insulin	X					
Clinical Labs: CBC and PT/INR, PTT		X				
Research Labs: AD Biomarkers, Cytokines/Chemokines, Neurotrophic Factors, Exosomes, Oxidative Stress Biomarkers, gene expression and DNA methylation, WBC differential counts, β -hydroxybuterate		X				
CSF		X			X	
Research Labs: β -hydroxybuterate, gene expression and DNA methylation, WBC differential counts, plasma sample for AD Biomarkers, Cytokines/Chemokines, Neurotrophic Factors, Exosomes, Oxidative Stress Biomarkers				X		
Clinical Labs: CBC with differential, CMP, HbA1c, Phosphate, Magnesium, TSH, Liver Panel, Lipid Panel, Uric Acid, PT/INR, PTT, insulin					X	
Research Labs: AD Biomarkers, Cytokines/Chemokines, Neurotrophic Factors, Exosomes, Oxidative Stress Biomarkers, gene expression and DNA methylation, WBC differential counts, insulin, β -hydroxybuterate					X	

Amount of Blood	28 ml	168 ml	62 ml/visit	174 ml
-----------------	-------	--------	-------------	--------

4.d.2. Baseline visit

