measurements (weight, waist circumference, sagittal diameter) will be done. Participants will provide feedback regarding physical and psychological symptoms by completing a Symptoms Review Questionnaire and the RAND SF-36. Samples for β -hydroxybutyrate levels will be sent to Harbor Hospital Lab. In addition, a plasma sample will be sent to the NIA Core Lab for future studies. These visits will take about 1 hour.

In addition, blood will be collected for isolation of total RNA and genomic DNA for target pathways gene expression and methylation analyses, and PBMCs counts. 62 ml of blood will be collected during each one of these visits.

4.d.5. Outcome visit

The Outcome Visit will occur at the end of the 8-week period in the 5-2 CR or control group. This visit will take place during the first of the two consecutive constriction days for 5-2 CR participants or at a convenient time during the week for control participants. This visit will occur after a 12-hour fast, to ensure comparability of the mixed meal test with the Baseline Visit. The visit procedures will be similar to the Baseline Visit, including a lumbar puncture (LP) and a medical history and physical exam.

Participants will arrive on the NIA-Clinical Research Unit after a 12-hour fast. The following procedures will be done: vital signs, anthropometric measurements (weight, waist circumference, sagittal diameter), and a blood draw for clinical labs (CBC, PT, PTT, INR, CMP, lipid panel, uric acid, HgbA1c, insulin, β -hydroxybutyrate), urine pregnancy test (only in women who are able to become pregnant), and research labs including DNA collection (for gene expression studies). A 4-hour mixed meal tolerance test will be done. They will also have cognitive testing and will be asked to complete the Symptoms Review Questionnaire, PANAS, and RAND SF-36. A lumbar puncture (LP) will take place and up to a total of 15 mL of CSF will be collected. Participants will also have a brain MRI. About 174 mL of blood will be taken during each visit (including clinical and research labs). To facilitate scheduling or satisfy a given participant's request, we may split the various procedures of the Outcome Visit over two days within a week from each other.

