Participants' genetic information will be kept confidential to the extent possible. The results of participants' genetic testing will be kept in a locked and secured manner at the NIH. Genetic information will not be part of participants' medical record. Genetic information about participants will not be revealed to others, including their relatives, without participants' written permission. Similarly, participants will not receive information about other family members.

Problems, such as with insurance or employment discrimination, may occur if participants disclose information about themselves or agree to have their research records released. We will not release any information about participants or their families to any physician, insurance company or employer unless you sign a document allowing release of the information.

Further discussion can be found under Section "20. Confidentiality" on pages 51-52.

7.o. Accelerometry: The accelerometer has no risks associated with its use and causes minimal inconvenience.

7.p. 5-2 CR/Control Diet: Overall, a minority of participants (9-15%) is expected to develop minor physical and psychological AEs during the first several weeks of 5-2 CR. Such AEs include lethargy, feeling cold, difficulty concentrating, and irritability. Participants may experience minor psychological symptoms such as feeling hungry (leading to preoccupation with food), lack of concentration, bad temper and irritability. The Harvie et al. study is especially important because our study design is similar to it. In the Harvie et al. study, a small number of participants on the 5-2 CR regimen (8%) reported physical symptoms including lack of energy, headaches, feeling cold, and constipation. Minor psychological symptoms included lack of concentration, bad temper, and a preoccupation with food among 15% of the 5-2 CR group. These adverse effects abated after cessation of CR. Conversely, 6% of 5-2 CR participants reported better health and increased energy.⁴⁰ Furthermore, 32% of 5-2 CR had increased self-confidence and positive mood. To minimize these risks, participants will be told ahead of time about potential side effects. During Compliance Visits, we will give participants the opportunity to discuss and will offer encouragement that may ameliorate minor psychological symptoms.

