- Any adverse event occurs Grade 2 or greater and possibly related to the study.
- The participant develops any of the exclusion criteria.
- There is persistent non-compliance with study requirements (keeping follow-up visits).

Participants will be informed about new information from this or other studies that may affect their health, welfare, or willingness to stay in this study. Participants may decide to stop participating at any time. Any data or blood collected until that point in time will remain part of the study and are the property of the National Institute on Aging.

9. Outcome measures

All secondary outcome variables in this pilot study are exploratory.

9. a. Primary outcome measures

- Exosomal p-S312-IRS-1/p-panY-IRS-1 ratio

9. b. Secondary outcome measures

- Other exosomal protein and mRNA biomarkers of AD;
- S_I and HOMA-IR, indices of insulin resistance, derived from insulin and glucose values taken from a fasting blood draw;
- fMRI activation to appetitive food versus non-appetitive food stimuli;
- Resting state fMRI intrinsic functional connectivity of DMN;
- Behavioral performance and fMRI activation during a Color-Word Stroop task;
- Brain metabolites assessed with Magnetic Resonance spectroscopy and regional perfusion assessed with arterial spin labeling;
- Memory and executive function scores.
- Anthropometric measures (weight, waist circumference, sagittal diameter);

- Clinical Labs: lipid panel, uric acid;
- Plasma ketones, such as β -hydroxybutyrate and other metabolites.
- Plasma metabolites and hormones (GLP-1, insulin) during a mixed meal test;
- CSF and plasma AD biomarkers, including $\text{A}\beta_{1-42}$ and p_{181}Tau ;
- Plasma and CSF neurotrophic factors, such as BDNF;
- Plasma and CSF reactive oxygen species, advanced glycation end-products and advanced oxidation protein products;
- Plasma and CSF pro-inflammatory cytokines, such as IL-6, IL-8, IL-12 and IL-23;
- Ratings of symptoms that can occur with 5-2 CR, mood and quality of life changes, recorded during both the 5-2 CR and control diet phases;
- Physical activity measured using an accelerometer.
- Global gene expression pattern, mitochondria gene expression and expression of other gene pathways responding to CR
- Genome-wide methylation in peripheral blood mononuclear cells

10. Statistical Analysis

10. a. Analysis of data/study outcomes

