This is a pilot study that is exploratory in nature and one of its goals is to collect preliminary data for multiple outcomes that may be used in future studies on the brain effects of CR.

For the primary and each secondary scalar measure, a separate repeated measures mixed models analysis will be conducted to examine the effects of the between-subjects factor “Group” (5-2 CR group vs. “Healthy living” control group), the within-subjects factor “Time” (Baseline vs. Outcome) and their Interaction. An Auto-Regressive (AR)1 covariance matrix and Restricted Maximum Likelihood Estimation (REML) will be used. We will assess fit to the model using the AIC and BIC criteria (lower values indicate better fit). These parameters were chosen because they are recommended for repeated measures analyses, including fMRI task analyses.¹⁰⁰ Regarding within-subjects effects, we will assess post-hoc differences between the 8-week outcome visit and baseline for the 5-2 CR and control groups and for each group separately (i.e. post-hoc tests for the Group * Time interaction). This analytic approach is common in the CR literature.¹⁰¹ Mixed model post-hoc tests will employ the Least Significant Difference (LSD) statistic. We will use one-tailed t-tests.

Criteria for significance will be set at alpha of 0.05 for all non-MRI analyses, and 0.005 uncorrected at the voxel level for fMRI analyses. Given that this pilot study is exploratory, we will not conduct correction of multiple comparisons for the various secondary outcomes.

Analysis of fMRI data will use a mixed model design to assess the effect of Group on

brain activation associated with viewing appetitive vs. non-appetitive food, the Stroop effect in the Stroop task, and DMN intrinsic functional connectivity. Analyses will be conducted at the whole brain level and within ROIs (vmPFC, OFC and insula for the fMRI food task, lateral and dmPFC for the Stroop task, and in DMN for resting state. The fMRI analyses will be corrected for type 1 error as the cluster level using Monte Carlo simulations.

For brain MRS measures, a repeated measures analysis will be separately used for each of the brain regions of interest: the hippocampus and the prefrontal cortex.

APOE genotype is a common covariate used when assessing populations with AD or at risk for AD. We intend to perform exploratory analyses including APOE, which may reduce error variance and improve our statistical models.

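### Symptoms, affect and quality of life are compared between arms only at Week 8, so early symptoms and all on-diet ratings from participants who leave go unused

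*Combined protocol and SAP*

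**What the plan says.** Section 10.a sets one analysis for all scalar outcomes: "For the primary and each secondary scalar measure, a separate repeated measures mixed models analysis will be conducted". Time has two levels, "Baseline vs. Outcome) and their Interaction", and on the follow-up tests the section says "we will assess post-hoc differences between the 8-week outcome visit and baseline". Section 9.b lists as a secondary outcome "Ratings of symptoms that can occur with 5-2 CR, mood and quality of life changes", so this model governs those ratings. No other analysis of them is given. Only the candidate-gene work in 10.a is tied to Compliance Visit samples.

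Much more is collected. Section 4.a.2 has symptoms asked about weekly. Section 4.d.4 has the Symptoms Review Questionnaire, RAND SF-36, weight, waist and sagittal diameter at Weeks 2, 4 and 6. Table 1 ticks PANAS and RAND SF-36 at those visits, but not the Symptoms Review Questionnaire. Table 2 also lists there a "plasma sample for AD Biomarkers, Cytokines/Chemokines, Neurotrophic Factors, Exosomes, Oxidative Stress Biomarkers", while 4.d.4 says "a plasma sample will be sent to the NIA Core Lab for future studies".

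On timing and leaving, section 7.p expects 9-15% of participants to "develop minor physical and psychological AEs during the first several weeks of 5-2 CR". Section 8.a ends participation if "Any adverse event occurs Grade 2 or greater and possibly related to the study", and anyone may withdraw. Sections 3.a, 4.a and 10.b replace those who leave until 40 participants have complete data. Section 8.a keeps leavers' data in the study but gives no analysis for them.

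**The concern.** A Week 8 contrast cannot stand in for the earlier visits. The symptom form covers the week before the visit (4.d.6), and PANAS asks about the present moment (Attachment D). Symptoms that appear in Week 2 and settle by Week 6 are invisible at Week 8 even if nobody leaves. If someone leaves at Week 3, the ratings already on file cannot enter a model with two time levels. A mixed model can keep that person's baseline row, but the row says nothing about how the diet was tolerated.

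Diet-related leaving is likelier in the 5-2 CR arm. Section 1 hypothesises that 5-2 CR improves affect and quality of life, 10.a tests one-tailed, and the pilot is meant to inform later studies. What is at stake is its message on tolerability: a reassuring Week 8 comparison could describe only the people who tolerated the diet.

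**Working it through.** **The plan's own figure.** No power or precision is given for symptoms, affect or quality of life. The only figure for the two-visit model is for the primary outcome (10.b): f = 0.3, N = 40, 2 measures, correlation 0.4. Noncentrality = 0.3² × 40 × 2 / (1 − 0.4) = 12 on 1 and 38 df. Power is 0.922 at alpha 0.05, or 0.961 one-sided. The stated figure of over 90% reproduces, and this point does not depend on it.

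**How many participants.** Assumption: the symptom rates in 7.p (8% physical in the cited similar study, 9-15% overall) are used as leaving rates. To finish with 20 in the 5-2 CR arm:
- 8%: 20 / 0.92 = 21.7, so 22 randomised; chance of at least one leaver among 20 = 1 − 0.92²⁰ = 81%
- 9%: 20 / 0.91 = 21.98, so 22; 1 − 0.91²⁰ = 85%
- 15%: 20 / 0.85 = 23.5, so 24; 1 − 0.85²⁰ = 96%

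The on-diet ratings of about 2 to 4 people would be unused.

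**Size on a 0-10 symptom item.** Assumption: affected participants have a lasting +3 and nobody else changes.
- True arm mean: 0.08 × 3 = +0.24; 0.15 × 3 = +0.45.
- Half of those affected leave: the Week 8 estimate is 3 × 0.04 / 0.96 = +0.12, or 3 × 0.075 / 0.925 = +0.24.
- All leave: the Week 8 estimate is 0. In a REML simulation of the two-visit model that kept leavers' baseline rows (SD 2, within-person correlation 0.4, 200 per arm, 25 runs), it was −0.04 for 8% and −0.02 for 15%. Both are zero within a simulation error of about 0.04.

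**What extra visits recover.** Suppose leavers go after Week 2, and use the same SD and an equal correlation of 0.4 between visits. The Week 2 difference comes back: +0.23 for 8% and +0.50 for 15% in the simulation, against true +0.24 and +0.45. Week 8 comes back only in part. The weight on each of two observed visits when predicting a third is 0.4 / 1.4 = 0.286, so the model returns 0.286 × 0.24 = +0.07 and 0.286 × 0.45 = +0.13. The simulation gave +0.03 and +0.11.

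The definition of the average on-diet difference also matters. Averaging the four visit-specific contrasts gives (0.24 + 3 × 0.07) / 4 = +0.11 and (0.45 + 3 × 0.13) / 4 = +0.21. Averaging each participant's own attended on-diet visits returns +0.24 and +0.45, because here the rise is lasting.

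**Weight.** Section 4.a.2 expects about 2% loss per week, so 2 × 2% = 4% in two weeks. Section 8.a starts closer monitoring of 5-2 CR participants at 4-5% in two weeks and removes those in whom loss in that range or greater continues. That rule takes out the largest losers. Section 1 reports about 8% over 8 weeks of alternate-day restriction, i.e. 1% per week, from the study that 4.a.2 cites for its 2%. How often the rule would apply is therefore unclear, and these passages should be reconciled.

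**The case against.** Tolerability is not left unrecorded. Adverse events are sought at every contact and recorded from consent to the end of participation (8.a), then summarised at Continuing Review (17). Leavers' data are kept, and all secondary outcomes are declared exploratory. This stands, and it rules out reading the plan as erasing leavers from the tolerability record. They are missing from the one planned arm comparison, and the adverse-event summaries do not replace it because no between-arm analysis of them is stated.

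The size is also open to challenge. Section 7.p calls the expected events minor, while removal needs Grade 2 or greater and possible relatedness, or the participant's own choice. So 8-15% leaving is an upper range, not a forecast. The shifts are small beside the noise: with SD 2 and correlation 0.4, the standard error of the arm difference in change at 20 per arm is 2 × √(2 × 0.6) × √(2/20) = 0.69. A reader might infer that the plan would manufacture an apparent improvement. The illustration does not show that: at worst the estimate falls to about 0.

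A reader might also infer that effects on weight or on the exosome ratio are inflated because poor responders leave. The documents do not support this. For weight, the 8.a rule works the other way. For the exosome ratio, nothing links leaving to a laboratory value that participants would not see.

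Finally, extra visits bring complications. 5-2 CR participants rate each item twice, for restricted and unrestricted days, and controls rate it once (Attachment E). Compliance Visits fall on the second restriction day for 5-2 CR but on any day for controls (4.d.4). These objections hold and shape the fix.

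**Conclusion.** The point holds for symptoms, affect and quality of life. The two-level Time factor leaves out all on-diet ratings before Week 8, and with them both early symptoms that settle and everything known about how leavers tolerated the diet. That much follows from the text without any assumption.

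The size rests on assumptions: 8% to 15% affected, a lasting +3 points, and all of them leaving. Then Week 8 shows about 0 against a true +0.24 to +0.45. With half leaving it shows about +0.12 to +0.24. If few leave, the loss is mainly of early, transient symptoms. For weight, data are lost in the same way, but the bias may run towards a smaller effect. As the outcomes are exploratory, this is an inexpensive improvement that should be made, not a flaw that invalidates the trial.

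**What to change.** In 10.a, for each outcome measured at Weeks 2, 4 and 6 (symptom ratings, PANAS, RAND SF-36, weight, waist, sagittal diameter):

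- Make Time a factor with all collected visits, and include every randomised participant up to the last visit attended.
- For symptoms, PANAS and RAND SF-36, report the average on-diet arm difference alongside Week 8. Say in advance whether it averages visit contrasts or each participant's attended visits. For body measures, report the Week 8 difference from the all-visit model.
- Report the number leaving by arm and reason, because extra visits recover only part of the Week 8 effect.
- State in advance how the 5-2 CR arm's two symptom ratings are combined for comparison with the single control rating, for example weighted 2:5, with each also shown.
- Reconcile Table 1 with 4.d.4 on which questionnaires are given at Compliance Visits. Also reconcile 4.d.1 with 4.d.5, which place the Outcome Visit on different restriction days; this matters for a momentary scale such as PANAS.

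Using stored Week 2-6 plasma for the exosome ratio is optional and supportive only, since those samples follow an 8-hour rather than a 12-hour fast.

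The cost is SAP wording and a little more analysis. The downside is that Week 2-6 PANAS scores in the 5-2 CR arm reflect a restriction day, which the report must state.

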Methylation in Leukocytes: There are two studies that have looked at genome-wide methylation in SAT and peripheral blood mononuclear cells (PBMCs) in humans.^{85,87} In the study of DNA methylation in SAT following 6-month CR, differences at 35 loci were found between the high and low weight loss responders at baseline suggesting methylation signature can be predictive of those who will respond to CR intervention. Three of these regions showed differential methylation after CR.⁸⁵ Not surprisingly, differential methylation was observed in genomic regions that contain genes linked with weight control and insulin regulation including the cholecystokinin B receptor gene. In the second study, differential methylation in PBMC was studied in 12 subjects who were either low- or high- weight loss responders to 8-weeks of caloric restriction.⁸⁷ At baseline, several CpG located in the aminophospholipid translocase (*ATP10A*) and cell surface glycoprotein 44 (*CD44*) genes differed between the two groups suggesting that methylation patterns in this region are important for weight loss in response to CR. At the end of the study, methylation differences were observed at the promoter region of Wilms tumor protein (*WT1*). Interestingly, the methylation at *ATP10A* and *WT1* significant changed during the 8-week intervention. The biological relevance of these genes with caloric restriction is unknown. One of the limitations of the study reported by Milagro and colleagues is that their analyses did not account for white blood cell differential counts. This is particularly concerning when studying weight loss since changes in leukocytes have been documented and shown to explain 10% of the variance in weight loss over 2 years.⁸⁸ Therefore, in our study, we intend to measure white blood cell and lymphocyte differential counts at the times of PBMCs acquisition. We expect to find a unique methylation signature with 5-2 CR in PBMCs. As with the expression data, we will use a two-pronged approach for the analysis of methylation data where we take a targeted candidate pathway approach and an agnostic genome-wide methylation change approach. Furthermore, our study may replicate some of the PBMC DNA methylation changes observed in CR findings reported by Milagro.⁸⁷

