White blood cell differential counts: The RNA and DNA used for the gene expression and methylation assay will be isolated from mixed population cells. The standard complete

blood count provides percentages of neutrophils, lymphocytes, monocytes, eosinophils and basophils. We will require further separation of lymphocytes to get the counts of T cells, B cells and natural killer cells. The distribution of white blood cells will be an important covariate in the analysis of gene expression and methylation to ensure that the associations that we observe is specific to 5-2 CR rather than changes in any of the cells during the dietary intervention. We will use cell specific monoclonal antibodies and flow cytometry to count the each cell population within the lymphocytes. The flow cytometry methods will require 5-10cc of whole blood.

4.e. End of participation

We will share with participants any new information that may relate to their willingness to continue to participate in this study. Within 3 days after the Week 8 Outcome Visit, either one of the investigators or nursing staff will contact the participant to assess whether there have been any problems since the visit. In addition, at the end of the Outcome visit, participants will be given an accelerometer to wear for 96 hours. They will be given instructions on how to wear the device and to mail it back to the unit via a pre-paid envelope. Completion of accelerometry and the final telephone or email communication mark the end of participation to the study.

Transfer of care or medical care offered at study completion is not applicable to this protocol, as the participants remain under the care of their primary health care providers.

We will discuss the results of physical examination, clinical lab tests, and structural MRI with participants and provide them relevant reports. We will encourage subjects to share any clinically significant information with their health care providers.

5. Management of Data and Samples

5.a. Storage

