Plasma ketones are strongly affected by alternate day CR acutely but not chronically;³⁹ our main objective for measuring them is to assess compliance with 5-2 CR.

We do not anticipate a change in physical activity in 5-2 CR versus “healthy living” control groups, because no change has been noted in our previous studies. Nonetheless, this is a common analysis requested by reviewers, to make sure that exercise effects did not contaminate diet effects.

The data from the gene array and DNA methylation array will be analyzed using residuals after adjustment for white blood cell differential count in linear regression models. We will take two approaches to analyze the data. First we will focus on candidate genes approach where we select specific expression probe or CpG sites; DNA for these studies will be collected during Baseline, Compliance and Outcome Visits. Second, we will run genome-wide association analysis for differences in cross sectional and longitudinal changes in gene expression or DNA methylation between the control and 5-2 CR group at each gene array probe or CpG site. DNA for genome-wide association analyses will only be collected during Baseline and Outcome Visits. For the cross sectional analyses, we will use a paired t-test at each visit, and mixed models for longitudinal analysis. In addition, we will look at overall patterns of gene expression and methylation using principle components, DIANE and hierarchical clustering tools to determine whether there are specific gene expression and methylation signature in association with 5-2 CR. As secondary analyses, we will also determine whether gene expression and DNA methylation patterns can predict the changes in metabolic, cognitive and neurochemical variables collected in this study. Within the 5-2 CR group, we will test the association between baseline levels of gene expression or DNA methylations at each probe/CpG site with longitudinal changes in the main outcome variables using mixed models.

10. b. Power analysis

The accrual number request is 100 participants. Our target sample size for completing the study is $N = 40$. There will be 20 participants in each group. We anticipate up to 60 participants will not meet inclusion criteria during the screening visit or may withdraw from the study. Enrollment will continue and withdrawals will be replaced until we have acquired complete data from 40 participants.

For power calculations, we used G*Power (<http://www.gpower.hhu.de/en.html>).

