Memory and Executive Function: Witte and colleagues⁶⁵ examined aged participants divided into groups that either engaged in 3 months of moderate (30%) CR ($n=20$), received no intervention ($n=10$), or received unsaturated fatty acid supplementation ($n=20$). For the Rey Auditory Verbal Learning Test, which is very similar to our CVLT, CR participants showed a significant 130% gain (Cohen's $d = 0.799$) in a composite memory score after the intervention versus non-significant changes in the other groups. Our own intervention only differs in the length of time spent on CR and the intermittent nature of the CR, and so we anticipate a comparable effect size. Given that executive function is more consistently impacted by obesity and by extension IR across the lifespan,^{105,106} we also anticipate a similar or greater effect size for executive function, although there are currently no studies in the literature directly comparable to our design. In summary, with an anticipated effect size $f = 0.4$, we will have power = 0.81 to detect an effect on cognition.

Plasma biomarkers: For plasma biomarkers, such as proinflammatory cytokines, ROS, BDNF, and affect measures, we note that our previous within-subjects study on intermittent CR in humans³⁹ produced robust differences in significant or near-significant trends in these measures by 3 mo. with $n = 42$ at alpha = .05. We anticipate being able to detect such effects and more subtle differences, because our between-subjects design is more powerful. In particular, informal power calculations suggest that we will have at least 80% power to detect differences in cytokines, ROS, and BDNF.

Global gene expression and genome-wide methylation: With sample size of 20 for each of the two groups, using the Illumina HT12 expression chip with 25,000 annotated genes, there is 80% power at alpha (two-tailed) = 0.05 to detect a 1.5-fold difference in expression. Similarly, with the sample size of the proposed study, we have 90% power to detect methylation differences of 40% between groups at alpha (two-tailed) = 0.05 for 45,000 CpG sites.

11. Human subjects protection

11. a. Subject selection

Statement of equitability

Participants will be recruited and enrolled equitably including, but not limited to,

without regard to race, ethnicity, sex, sexual orientation, unless explained below.

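### Comparing arms on array residuals already adjusted for white-cell counts shrinks the single-visit diet effect and can bias the longitudinal one either way; model Group and counts together

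*Combined protocol and SAP*

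**What the plan says.** Section 10.a (Analysis of data/study outcomes) says that gene-array and methylation-array data will be analysed "using residuals after adjustment for white blood cell differential count in linear regression models". Arms are then compared at each visit, and mixed models are used for longitudinal change. The same paragraph plans principal components, clustering and prediction within the 5-2 CR arm. It does not say whether Group or Time is in the first regression, or how the degrees of freedom spent there are counted.

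Section 4.d.6 (White blood cell differential counts) gives the purpose: "The distribution of white blood cells will be an important covariate in the analysis of gene expression and methylation", so that an association reflects 5-2 CR "rather than changes in any of the cells during the dietary intervention". The available counts are "percentages of neutrophils, lymphocytes, monocytes, eosinophils and basophils", with lymphocytes split further into T, B and natural killer cells. The exact covariate set is not named.

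Section 1 (Methylation in Leukocytes) explains why counts matter in weight-loss studies: "changes in leukocytes have been documented and shown to explain 10% of the variance in weight loss over 2 years".

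Section 10.b (Power analysis) states "There will be 20 participants in each group", and for expression claims that "there is 80% power at alpha (two-tailed) = 0.05 to detect a 1.5-fold difference in expression". Section 9 labels all secondary outcomes, which include the arrays, as exploratory.

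**The concern.** Residualising the outcome on the counts removes any part of the diet effect that overlaps with the counts. Group itself is not residualised, so the second step divides what is left by the full variation in Group. The result is neither the total diet effect nor the cell-adjusted effect that section 4.d.6 asks for.

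Section 10.a says that one goal of this pilot is preliminary data for later studies. Fold changes and methylation differences are what a later study would be sized on, so a distorted effect size matters even where the test itself is little affected. The arms are also expected to differ in weight loss: the studies cited under Rationale for control condition (section 4.a.1) report 6.5 kg with 5-2 CR and 0.6 kg with counselling. An arm difference in week-8 counts is therefore plausible, although none is quantified.

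**Working it through.** **Inputs from the documents.** N = 40, 20 per arm. Number of counts k: section 4.d.6 allows neutrophils, monocytes, eosinophils, basophils, T, B and NK cells, so at most 7. Percentages make one category redundant and the set is not named, so I use k = 4 to 7.

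**Assumptions not in the documents.** The SD of log2 expression, the arm shift in counts and the slopes of expression on counts. Section 10.a calls the per-visit test paired; the arms are different people, so I use an unpaired comparison.

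**The plan's own figure.** log2(1.5) = 0.585. With 20 per arm and two-sided 0.05, 80% power needs a standardised difference of 0.909, which implies an SD of 0.585/0.909 = 0.643. No SD is stated, so the 80% can be solved backwards but not reproduced independently. I carry 0.909 forward as the true effect.

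**Single visit.** Let g be Group (centred), y the probe value and M the residual-maker for the counts.

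- Joint model: b_joint = g′My / g′Mg.
- Residuals compared by arm: b_res = g′My / g′g.
- Ratio: b_res / b_joint = g′Mg / g′g = 1 − R², with R² from regressing Group on the counts.

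This is algebra, and it held to rounding error in every simulated trial. If the counts are unrelated to Group, the expected R² is k/(N − 1): 4/39 = 0.10 and 7/39 = 0.18.

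Simulation, 6,000 trials per setting, true effect 0.909 residual SD, one count shifted between arms (residual method / joint model):

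| k | shift (SD) | mean R² | mean estimate | SD of estimate | RMSE | power | type I error, residual method |
|---|---|---|---|---|---|---|---|
| 4 | 0 | 0.10 | 0.82 / 0.91 | 0.30 / 0.33 | 0.32 / 0.33 | 75% / 76% | 5.5% |
| 4 | 1.0 | 0.28 | 0.65 / 0.90 | 0.29 / 0.38 | 0.39 / 0.38 | 54% / 64% | 2.9% |
| 7 | 0 | 0.18 | 0.74 / 0.90 | 0.29 / 0.35 | 0.34 / 0.35 | 70% / 71% | 5.0% |
| 7 | 0.5 | 0.23 | 0.70 / 0.91 | 0.29 / 0.36 | 0.36 / 0.36 | 65% / 69% | 4.1% |
| 7 | 1.0 | 0.34 | 0.60 / 0.91 | 0.27 / 0.40 | 0.41 / 0.40 | 50% / 61% | 3.0% |

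In fold-change terms with k = 7: no shift gives 2^(0.585 × 0.74/0.909) = 1.39; a 1 SD shift gives 2^(0.585 × 0.60/0.909) = 1.31. The truth is 1.5 in both.

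**Two visits, Group-by-Time.** Suppose the residuals come from one pooled regression with slope b_pool. The arm difference in mean residual change is then

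D(Y) − b_pool·D(X),

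where D is the arm difference in mean change. The cell-adjusted effect is D(Y) − b_within·D(X), so

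bias = (b_within − b_pool)·D(X).

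Its sign depends on whether the pooled slope is steeper or flatter than the within-person slope. With a true effect of 0.90 and D(X) = 1 SD, simulation gave:

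- Simplest case: 0.75 (bias −0.15).
- Common time effect of −1.5 and common count change of 0.5 added: 1.01 (bias +0.11).
- Between-person slope 0, within-person slope 0.5: 1.00 (bias +0.10).

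Across other assumed slopes and trends the residual estimate ran from 0.44 to 1.12.

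A joint random-intercept model with a single count slope is not safe either. It gave 1.14 with between-person slope 0 and within-person slope 0.5, and 0.65 with between-person slope 1.0. Regressing change in the outcome on Group and change in counts gave 0.88 to 0.91 in every setting.

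**The case against.** **The omission of Group is inferred.** Section 4.d.6 calls the counts a covariate, which would fit a joint model. This stands as an ambiguity, but the statistical section describes residuals. Ordinary residuals from a model containing Group would leave no arm difference to test. If only the count component were subtracted, using slopes from a model with Group, the estimate would be right, but a plain two-sample standard error would be too small because it ignores R². Each reading needs a change or a clarification.

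**The joint model has a price.** A reader might infer that it is free. It is not: its SD is larger in every row above, it uses k of the 38 degrees of freedom (31 remain with k = 7), and with no shift its RMSE is slightly higher. What it does not lose is single-visit power against the residual method.

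**Residuals do not always bias toward zero.** A reader might infer this from the single-visit algebra. The identity does not carry over to the planned longitudinal analysis, where the sign can reverse.

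**No arm difference in counts is documented.** The cited 10% relates leukocyte changes to weight loss over two years. It does not say how far 5-2 CR moves counts relative to control at eight weeks, so only the chance shrinkage rests on the plan's own numbers.

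**Week-8 counts are post-randomisation.** Adjusting for them gives a cell-adjusted effect, not the total diet effect. That matches section 4.d.6 but has to be stated.

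**Residuals have a proper use.** Principal components and clustering can reasonably be run on them, and a per-probe arm model does not replace those analyses.

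**Conclusion.** The concern holds for the per-probe and per-CpG arm comparisons, on the reading that the first regression omits Group. At a single visit the cell-adjusted effect is shrunk by exactly 1 − R²: about 10% to 18% by chance for 4 to 7 counts and N = 40. In that chance-only case the test stays close to nominal and power is practically unchanged, so the damage is to the effect size. If the diet shifts counts, shrinkage grows, the test becomes conservative and power is lost; how much depends on shifts that I have assumed.

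For Group-by-Time the finding is bias of unpredictable sign, shown for two visits only; the candidate-gene analysis also uses the compliance visits. The primary outcome does not use this method and is unaffected. This is a worthwhile improvement to exploratory analyses, not a threat to the trial's main conclusion.

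**What to change.** Amend the array paragraph of section 10.a as follows:

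1. **Single-visit comparisons.** Fit one linear model per probe or CpG containing Group and the cell counts, and test Group from that model with its own residual degrees of freedom. Name the counts and drop one category if percentages are used.
2. **Longitudinal analysis.** Fit Group, Time, Group × Time and the counts, entering each count as the person mean and the within-person deviation from it. Test Group × Time. With two visits, regressing change in expression or methylation on Group and change in counts is a simple alternative.
3. **Estimand.** State that this is a cell-adjusted effect because follow-up counts are post-randomisation, and report the unadjusted effect beside it.
4. **Residuals.** Keep them, if wanted, for the principal-component and clustering analyses.

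The cost is analysis code only. Table 2 already schedules differential counts at the baseline, compliance and outcome visits. The statistical price is a wider standard error and about 4 to 7 degrees of freedom, with no loss of power against the residual method in the single-visit comparison.
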